###### 4.5.4.1.3 Available biopsy at V3 (Week 24)

Biopsy will be considered as available at Week 24 if SAF-A is non-missing for a biopsy reported at V3 (or for a re-test of a biopsy reported at V3). It will be considered as non-available in all other cases.

Reason for non-availability will be considered as:

- “Treatment Prematurely Withdrawn” for all non-completers patients
- "Non-Readable" if biopsy has been performed at V3 and SAF-A is missing for any completer patient
- “Patient Refusal" if reason for not having performed a biopsy at Visit 3 contains ("NOT AGREE" "REFUS" "NOT WANT") for any completer patient

###### 4.5.4.1.4 Terminology

In the biopsy database, several scores are provided including:

- The SAF Steatosis score (SAF-S) and the CRN Steatosis score (CRN-S) that are similar
- The SAF Lobular Inflammation score (SAF-I) and the CRN Lobular Inflammation score (CRN-I) that may slightly differ. Indeed, score of 1 for SAF-I could be grade 2 for CRN-I.

- The Hepatocyte Ballooning score, considered as the CRN Hepatocyte Ballooning score (CRN-B)
- The SAF Activity score (SAF-A) that is already derived in the database, and that corresponds to the sum of SAF-I and CRN-B
- The CRN NAS score (NAS) that will be defined as the NAS score (NAS). This parameter is already derived in the database, and corresponds to the sum of CRN-S, CRN-I and CRN-B
- The SAF Fibrosis score (SAF-F) and the CRN Fibrosis score (CRN-F) that may slightly differ. Indeed values 1a 1b and 1c for the CRN-F are graded as 1 for SAF-F. In the analyses, stages 1a 1b and 1c for CRN-F will be considered as stage 1.

#### 4.5.4.1.5 *Biopsy length*

Available biopsy length will be classified as  $\leq 8$  mm or  $> 8$  mm.

#### 4.5.4.1.6 *Response according to SAF activity score (Primary endpoint)*

Response is defined as a decrease from baseline to Week 24 of at least 2 points of the SAF Activity score (SAF-A) without worsening of the CRN Fibrosis score (CRN-F). No worsening means that score remains stable or decreases.

#### 4.5.4.1.7 *NASH improvement*

Improvement is defined as a decrease of at least 2 points of the NAS score (NAS) from baseline to Week 24 without worsening of the CRN Fibrosis score (CRN-F).

#### 4.5.4.1.8 *Resolution of NASH without worsening of fibrosis*

Resolution of NASH at Week 24 without worsening of fibrosis is defined as:

- CRN Lobular inflammation score (CRN-I) equal to {0, 1} at week 24 and
- CRN Hepatocyte ballooning score (CRN-B) equal to 0 at week 24 and
- No worsening of the CRN-F score from baseline to week 24.

#### 4.5.4.1.9 *Improvement of liver fibrosis $\geq 1$ stage and no worsening of NASH*

Improvement of liver fibrosis  $\geq 1$  stage and no worsening of NASH is defined from baseline to week 24 as:

- Improvement of CRN-F score  $\geq 1$  stage and
- No increase of CRN-S score and
- No increase of CRN-I score and

- No increase of CRN-B score

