***Secondary endpoints:***

The following changes from baseline to 24 weeks of treatment will be evaluated:

- NASH improvers defined as subjects with a decrease of at least 2 points in NAS, and no worsening in fibrosis from baseline to end of treatment (week 24).
- Percent of patients with resolution of NASH (Steatosis without ballooning and with or without mild inflammation) and no worsening of fibrosis) from baseline to end of treatment (week 24).
- Percent of patients with a change in components of SAF score from baseline to end of treatment (week 24):
  - Steatosis: -1 point
  - Lobular inflammation: -1 point
  - Ballooning: -1 point
- Percent of patients with at least 1- point improvement of fibrosis score on a 4-point scale (SAF) without worsening of NASH, defined as no increase for ballooning, or inflammation, or steatosis, using the SAF scoring system, from baseline to end of treatment (week 24).
- Change in fibrosis score on a 4-points scale (SAF) and modified Ishak: - 1 point from baseline to end of treatment (week 24).
- Liver enzymes (ALT, AST,  $\gamma$ GT) change from baseline to end of treatment (week 24).
- Inflammatory markers (fibrinogen, hs-CRP, alpha2 macroglobulin and haptoglobin levels) change from baseline to end of treatment (week 24).
- Glucose metabolism (fasting glucose and insulin, HOMA index and, in subjects with T2DM, HbA1c) change from baseline to end of treatment (week 24).
- Main plasma lipids levels (TC, HDL-C, calculated LDL-C, TG and apoA1) change from baseline to end of treatment (week 24).
- Adiponectin change from baseline to end of treatment (week 24).

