# 9. **Statistical Methods**

## 9.1 **Efficacy Assessments**

**Primary endpoint:** The primary efficacy endpoint will be a binary variable (responder / non-responder) based on the change from baseline to Week 24 of the SAF activity score. Responder is defined as a decrease from baseline to week 24 of at least 2 points of the SAF activity score combining hepatocellular inflammatory and ballooning without worsening of fibrosis. Any stage increase of fibrosis is considered fibrosis progression. The main question of interest is: “Does at

least one of the two doses increases the percentage of responders compared to placebo?”. The main comparison of interest is therefore each of the two verum groups versus placebo.

**Secondary endpoints:** The following changes from baseline to 24 weeks of treatment will be evaluated:

- Percent of patients with resolution of NASH (Steatosis with or without mild inflammation and no worsening of fibrosis) from baseline to end of treatment (week 24).
- Percent of patients with a change in components of SAF score from baseline to end of treatment (week 24):
  - Steatosis: -1 point
  - Lobular inflammation: -1 point
  - Ballooning: -1 point
- Percent of patients with at least 1-point improvement of fibrosis score on a 4-point scale (SAF) without worsening of NASH, defined as no increase for ballooning, inflammation, or steatosis, using the SAF scoring system, from baseline to end of treatment (week 24).
- Change in fibrosis score on a 4-points scale (SAF) and modified Ishak: - one point from baseline to end of treatment (week 24).
- Liver enzymes (ALT, AST,  $\gamma$ GT) change from baseline to end of treatment (week 24).
- Inflammatory markers (fibrinogen, hs-CRP, alpha2 macroglobulin and haptoglobin levels) change from baseline to end of treatment (week 24).
- Glucose metabolism (fasting glucose and insulin, HOMA index and, in subjects with T2DM, HbA1c) change from baseline to end of treatment (week 24).
- Main plasma lipids levels (TC, HDL-C, calculated LDL-C, TG and apoA1) change from baseline to end of treatment (week 24).
- Adiponectin change from baseline to end of treatment (week 24).

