## APPENDIX C: LIVER BIOPSY AND HISTOLOGY METHODS

### 1. THE SAF SCORING SYSTEM

The SAF assesses both and separately the grade of steatosis (S), the grade of activity (A), and the stage of fibrosis (F), the latter according to the NASH Clinical Research Network (CRN)(76). Steatosis is assessed by the percentage of hepatocytes containing large and medium-sized intracytoplasmic lipid droplets (but not foamy microvesicles), on a scale of 0 to 3 (S0: <5%; S1: 5%-33%, S2: 34%-66%, S3:>67%). Ballooning of hepatocytes is graded from 0 to 2 (0: normal hepatocytes with cuboidal shape, sharp angles and pink eosinophilic cytoplasm; 1: presence of clusters of hepatocytes with a rounded shape and pale cytoplasm, usually reticulated where, although the shape is different, the size is similar to that of normal hepatocytes; 2, as for grade 1, but where there was also at least one enlarged ballooned hepatocyte (at least 2-fold size compared with that of normal cells within a cluster of hepatocytes with grade 1 ballooning). Lobular inflammation is defined as a focus of two or more inflammatory cells within the lobule organized either as microgranulomas or located within the sinusoids. Foci are counted at 20x magnification (grade 0: none; 1: < 2 foci per lobule; 2: >2 foci per lobule). The grade of activity (A from A0 to A4) is calculated by addition of grades of ballooning and lobular inflammation. Aspects of grading are illustrated Figure 5.

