### 4.6.3 Endpoints

Some additional information have been added in the SAP in order to clearly explain which biopsies should be taken into account for efficacy analysis at week 24 (cases of biopsies with multiple reading, efficacy vs. safety biopsies, definition of available biopsies): see sections 4.5.4.1.1 to 4.5.4.1.3.

The following secondary endpoints have been added:

- NASH improvement (see section 4.5.4.1.7)
- Resolution of NASH and Improvement of liver fibrosis  $\geq 1$  stage (see section 4.5.4.1.10)
- Resolution of NASH without worsening of fibrosis and NASH improvement (see section 4.5.4.1.11)
- Improvement of ISHAK liver fibrosis  $\geq 2$  stages and no worsening of NASH (see section 4.5.4.1.12)
- Fibrosis markers: NAFLD Fibrosis Score (NFS), FIB-4 score, ELF Score, MACK-3 Score, FIB3 Score and ABC3D Score (see section 4.5.4.2)
- No worsening of CRN-F score and modified Fibrosis Ishak score (modified ISHAK-F)

The analysis of the following parameters has been added too:

- Quality of Life: SF-36 and Flinders Fatigue scale (FFS)

- Pharmacokinetic data

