#### *5.2.3.6 Change in components Steatosis (CRN-S), Activity (SAF-A), Inflammation (CRN-I) and Ballooning (CRN-B)*

##### *5.2.3.6.1 Improvement*

The endpoints are the following components: CRN-S, CRN-I and CRN-B scores. For each component, the following variable will be considered based on the change from baseline to Week 24:

- Improvement of at least 1 point change of the component (Yes, No)

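### The SAP scores inflammation on the CRN scale in two secondary endpoints that protocol v5.0 defines on the SAF scale, and SAP 4.6 does not record the change

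*SAP*

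**What the plan says.** **Protocol v5.0.** The synopsis asks for at least one stage of fibrosis improvement "without worsening of NASH, defined as no increase for ballooning, or inflammation, or steatosis, using the SAF scoring system". Section 9.1 repeats the condition: "defined as no increase for ballooning, inflammation, or steatosis, using the SAF scoring system". A separate secondary endpoint, in both places, is "Percent of patients with a change in components of SAF score from baseline to end of treatment (week 24". The entries under it are steatosis, lobular inflammation and ballooning, each at minus 1 point.

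**SAP.** In section 4.5.4.1.9, one of the conditions for absence of NASH worsening reads "No increase of CRN-I score and", alongside matching conditions on CRN-S and CRN-B. For the component endpoint, section 5.2.3.6.1 says "The endpoints are the following components: CRN-S, CRN-I and CRN-B scores". Section 4.5.4.1.4 notes that the two inflammation scores are not identical: "Indeed, score of 1 for SAF-I could be grade 2 for CRN-I".

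**Declared changes.** SAP 4.6 is the section for departures from the protocol's statistical section. Its endpoint list (4.6.3) begins "The following secondary endpoints have been added". Neither that list nor the rest of 4.6 mentions replacing SAF-I by CRN-I.

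**The concern.** Both definitions feed main analyses: full analysis set, missing counted as non-response, and a stratified CMH test of each dose against placebo (SAP 5.2.3.3 and 5.2.3.6.1). If the scales disagree for a patient, the tested result is not the one the protocol defined.

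The protocol versions would not appear elsewhere either. SAF-I is only tabulated at baseline (SAP 5.1.7) and at week 24 (SAP 5.5.1). The change tables in 5.2.3.6.2 cover CRN-S, SAF-A, CRN-I and CRN-B, but not SAF-I. A reader who relied on 4.6 to learn what had changed would assume that the protocol definitions still stood.

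**Working it through.** The plan gives no figure on this point. Its sample size calculation concerns the primary endpoint and is not an input. The check therefore compares the two definitions pattern by pattern.

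**1. Which components can differ.** SAP 4.5.4.1.4 treats the two steatosis scores as similar, uses a single ballooning score, and collapses CRN fibrosis stages 1a to 1c into stage 1. Only inflammation is left. The primary endpoint (SAP 4.5.4.1.6) uses SAF-A and does not change.

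**2. Ranges.** SAF-I runs from 0 to 2. Protocol Appendix C gives "Foci are counted at 20x magnification (grade 0: none; 1: < 2 foci per lobule; 2: >2 foci per lobule". The biopsy form in the same appendix scores CRN inflammation separately, from 0 to 3. SAP 5.1.7 and 5.5.1 list CRN-I only up to 2, but their NAS range of 0 to 8 needs 3 + 3 + 2 = 8; with CRN-I capped at 2 the maximum would be 3 + 2 + 2 = 7. Both readings are covered below.

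**3. Baseline.** Eligibility requires SAF-A of at least 3 and ballooning is at most 2, so baseline SAF-I is at least 3 − 2 = 1.

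**4. Using only the overlap the SAP documents** (SAF-I 1 may be CRN-I 1 or 2):

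| SAF-I | CRN-I | Condition | Protocol v5.0 | SAP |
|---|---|---|---|---|
| 1 to 1 | 1 to 2 | inflammation not worse | met | not met |
| 1 to 1 | 2 to 1 | inflammation improved | no | yes |

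**5. If SAF-I 2 may also be CRN-I 2 (an assumption)**, the opposite reclassification is possible. SAF-I 1 to 2 with CRN-I 2 to 2 is worse under the protocol only. SAF-I 2 to 1 with CRN-I 2 to 2 is improved under the protocol only.

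**6. Counting patterns.** Each eligible baseline state is paired with each week-24 state. SAF-I 0 is taken as CRN-I 0, and SAF-I 1 as CRN-I 1 or 2.

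| Assumed CRN-I for SAF-I 2 | Possible patterns | Discordant, not worse | Discordant, improved |
|---|---|---|---|
| 3 only | 3 × 4 = 12 | 1 | 1 |
| 2 only | 3 × 4 = 12 | 2 | 2 |
| 2 or 3 | 4 × 5 = 20 | 3 | 3 |

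The scales disagree under every mapping tried. These are counts of possible patterns, not patient frequencies.

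**7. Effect of one patient.** At the planned 75 per arm, 1/75 = 1.3 percentage points. With 247 randomised (SAP 3.5), 247/3 is about 82 per arm, and 1/82 = 1.2 points. Four patients in one arm would move its rate by 4/82 = 4.9 to 4/75 = 5.3 points.

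**The case against.** **The SAP is open about the scale.** CRN-I is named in the endpoint definition, in the 5.2.3.6 heading and in the summary table, and 4.5.4.1.4 says the scales may differ. This stands: a reader might infer concealment, and the documents do not support that. What is missing is an entry in 4.6 and the SAF-I result.

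**The protocol lets the SAP prevail.** Protocol 9.7.4 gives precedence to SAP clarifications unless they cause major inconsistencies. Replacing a scale that the protocol names goes beyond clarification, so the clause does not settle the matter.

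**The governing protocol is v5.1.** Only v5.0 was supplied, so a changed definition cannot be excluded. SAP 4.6.3 lists NASH improvement as added, which fits its absence from the v5.0 section 9.1 list. That suggests the list was carried over unchanged, but does not prove it. This limits confidence.

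**The practical effect may be small.** On the fibrosis endpoint a patient is reclassified only if fibrosis improves, steatosis and ballooning do not worsen, and inflammation falls in a discordant pattern. This is fair, and no frequency is available to answer it.

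**CRN-I is used consistently in the SAP**, and the protocol itself borrows CRN staging for fibrosis. Declaring CRN-I in 4.6 with a SAF-I sensitivity analysis would cure the non-declaration. It would still leave the main result on a scale that v5.0 did not specify.

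**Conclusion.** The point holds against protocol v5.0. Two secondary endpoints defined on SAF inflammation are analysed on CRN inflammation, the SAP acknowledges that the scales differ, the change is not recorded in 4.6, and no planned analysis recovers the SAF-I versions. The documented overlap alone is enough to change responder status on each endpoint.

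The size is unknown. The documents give no joint distribution of SAF-I and CRN-I, and reclassification in the opposite direction rests on an assumed mapping. A reader might take the pattern counts as a share of patients, or infer a bias towards lanifibranor; neither can be supported.

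A reader might also extend the point to NASH resolution. That is a protocol endpoint, but the protocol names no inflammation scale for it, so scoring it on CRN-I contradicts nothing. The primary endpoint and the steatosis, ballooning and fibrosis components are not affected.

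**What to change.** 1. Check how protocol v5.1 words the two endpoints.
2. If the wording is unchanged, use SAF-I for inflammation in the main analysis of SAP 4.5.4.1.9 and 5.2.3.6.1, with the CRN-I versions kept as sensitivity analyses.
3. Add SAF-I to the change tables in 5.2.3.6.2.
4. Give the SAP-added Ishak endpoint (4.5.4.1.12) the same definition of no worsening of NASH, or label it as CRN-based, so that one phrase does not carry two meanings.
5. Record all of this in SAP 4.6.3. NASH resolution may stay on CRN-I.

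The cost is one extra derived variable and a few tables. SAF-I is already in the biopsy database, so no slide has to be read again.

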#### 4.5.4.1.10 Resolution of NASH and Improvement of liver fibrosis $\geq 1$ stage

Resolution of NASH and Improvement of liver fibrosis  $\geq 1$  stage is defined as:

- CRN Lobular inflammation score (CRN-I) equal to {0, 1} at week 24 and
- CRN Hepatocyte ballooning score (CRN-B) equal to 0 at week 24 and
- Improvement of CRN-F score  $\geq 1$  stage from baseline to week 24

#### 4.5.4.1.11 Resolution of NASH without worsening of fibrosis and NASH improvement

Resolution of NASH at Week 24 without worsening of fibrosis and NASH improvement are defined as:

- CRN Lobular inflammation score (CRN-I) equal to {0, 1} at week 24 and
- CRN Hepatocyte ballooning score (CRN-B) equal to 0 at week 24 and
- Decrease of at least 2 points of the NAS score (NAS) from baseline to week 24
- No worsening of the CRN-F score from baseline to week 24.

#### 4.5.4.1.12 Improvement of ISHAK liver fibrosis $\geq 2$ stages and no worsening of NASH

Improvement of ISHAK liver fibrosis  $\geq 2$  stages and no worsening of NASH is defined from baseline to week 24 as:

- Improvement of ISHAK-F score  $\geq 2$  stages and
- No increase of CRN-S score and
- No increase of CRN-I score and
- No increase of CRN-B score

### 4.5.4.2 Fibrosis markers

#### 4.5.4.2.1 NAFLD Fibrosis Score (NFS)

NAFLD Fibrosis Score is to be calculated using the following formula:  $-1.675 + 0.037 * \text{age (years)} + 0.094 * \text{BMI (kg/m}^2) + 1.13 * (\text{Impaired Fasting Glucose/diabetes (yes = 1, no = 0)}) + 0.99 * (\text{AST/ALT ratio (no unit)}) - 0.013 * \text{platelets (}\times 10^9/\text{L)} - 0.66 * \text{albumin (g/dl)}$   
(See Reference 2)

The variable '*Impaired Fasting Glucose/diabetes (yes = 1, no = 0)*' corresponds to the insulin-resistant status (Yes, No).

A variable predicting the fibrosis will be constructed from the NFS:

- Low probability of fibrosis F3/F4 if score is less or equal to -1.455 (included),
- Fibrosis status indeterminate if  $-1.455 < \text{score} < 0.676$ ,

- High probability of fibrosis F3/F4 if score is greater or equal to 0.676 (included).

#### 4.5.4.2.2 FIB-4 score

FIB-4 score is to be calculated using the following formula:  $(age \text{ (years)} * AST \text{ (U/L)}) / (platelets \text{ (}\times 10^9/L) * \sqrt{ALT \text{ (U/L)}})$   
(See Reference 3)

A variable predicting the fibrosis will be constructed from the FIB-4 score:

- Low probability of fibrosis F3/F4 if score is less to 1.45 (excluded),
- Fibrosis status indeterminate if  $1.45 \leq \text{score} \leq 3.25$ ,
- High probability of fibrosis F3/F4 if score is greater to 3.25 (excluded).

#### 4.5.4.2.3 ELF Score

ELF score is to be calculated using the following formula:  $2.494 + 0.846 \ln(\text{Hyaluronic acid}) + 0.735 \ln(\text{PIIINP}) + 0.391 \ln(\text{TIMP-1})$   
(See Reference 4)

A variable predicting the fibrosis will be constructed from the ELF:

- A score less than 7.7 (excluded) indicates no to mild fibrosis
- A score between 7.7 (included) and 9.8 (excluded) indicates moderate fibrosis
- A score between 9.8 (included) and 11.3 (excluded) indicates severe fibrosis
- A score greater or equal to 11.3 (included) indicates cirrhosis.

#### 4.5.4.2.4 MACK-3 Score

MACK-3 score is to be derived using the computation tool available at the website <http://forge.info.univ-angers.fr/~gh/wstat/mack3-calculator.php> (last access on 16JAN20120).

The score is based on the following parameters: AST (IU/L), Glycaemia (mmol/l), Insulin ( $\mu\text{U/ml}$ ) and Cytokeratin M30 (IU/L).

(See Reference 6)

A variable predicting the fibrosis will be constructed from the MACK-3 score:

- If Non metabolic syndrome and  $AST < 35 \text{ IU/L}$ : No fibrosis
- If Metabolic syndrome and/or  $AST \geq 35 \text{ IU/L}$ :
  - Score less or equal than 0.134 (included): No fibrosis
  - Score between 0.135 (included) and 0.549 (included): Fibrosis undefinable (grey zone)
  - Score greater or equal to 0.550 (included): Fibrosis

#### 4.5.4.2.5 FIBC3 Score

FIBC3 score is to be calculated using the following formula:  $-5.939 + (0.053 * \text{Age in years}) + (0.076 * \text{BMI in kg/m}^2) + (1.614 * \text{T2DM (yes = 1, no = 0)}) - (0.009 * \text{platelets in } 10^9/\text{L}) + (0.071 * \text{PRO-C3 in ng/ml})$   
 (See Reference 8)

#### 4.5.4.2.6 ABC3D Score

The derived “ABC3D” score comprises: A = Age>50 years, B = BMI>30 kg/m^2, C = platelet Count<200x10^9/L, 3 = PRO-C3>15.5 ng/ml, D = Diabetes = present.  
 The presence of each factor scores 1 point, except for T2DM that scores 2 points, yielding to a maximum of 6 (See Reference 8)

#### 4.5.4.3 Glucose metabolism

Available HOMA index will be classified as < 3 or ≥ 3.

#### 4.5.5 Questionnaires

[figure not shown]
##### 4.5.5.1 Short Form Health Survey (SF-36)

#### **Purpose:**

SF-36 is a set of generic, coherent, and easily administered quality-of-life measures. These measures rely upon patient self-reporting and are now widely utilized by managed care organizations and by Medicare for routine monitoring and assessment of care outcomes in adult patients.

#### **Description:**

The SF-36 is “a multi-purpose, short-form health survey with only 36 questions”. It yields an 8-scale profile including functional health, and mental health.

#### **Derivation:**

A specific tool will be provided with the SF-36 questionnaire to calculate the score of the 8 sub-dimensions defined above, as well as the physical component score (PCS) and mental component score (MCS). Each score will be norm-based from 0 to 100.

**Interpretation:**

All questions are scored on a scale from 0 to 100, the minimum score is 0 (corresponding to a poor health) and maximum is 100 (corresponding to a good health).

**Reference:**

QualityMetric Health Outcomes Scoring Software User's guide

*4.5.5.2 Flinders Fatigue Scale (FFS)*

**Purpose:**

The FSS is a self-report questionnaire, designed to measure daytime fatigue.

**Description:**

It is a relatively brief measure, containing only 7 items that provide a global measure of fatigue.

Each item ranks from 0 (not at all) to 4 (extremely), except item 5 for which patient need to tick the time(s) of the day where fatigue is experienced (among 7 possible times).

**Derivation:**

Global score can be calculated by summing scores on all items as 0 (not at all) through 4 (entirely), except for item 5 (for this item, sum each time of day that is ticked).

**Interpretation:**

Global score ranges from 0 to 31 and higher scores indicate greater fatigue.

The compliance (%) for a given visit is defined as:

$$\Rightarrow \text{Total number of tablets taken between study first treatment intake to } V_i / \text{Total number of tablets to be received between study first treatment intake to } V_i * 100$$

- **Overall persistence**

The persistence (%) corresponds to the ratio between the actual number of tablets taken and the expected number of tablets to be received between the study first treatment intake and last treatment intake.

Tablets taken:

The total number of tablets taken corresponds to the sum of the number of tablets taken in each bottle at each visit.

See definition above (in section Compliance at Visit(i)).

Tablets to be received:

The total number of tablets to be received is equal to:

$$(\text{Study last treatment intake date} - \text{Study first treatment intake date} + 1) * 3$$

- **Overall compliance at time of biopsy at week 24 (when biopsy results at week 24 are available)**

Overall compliance can be calculated as the ratio between actual number of tablets taken between first intake and time of biopsy at week 24, and the theoretical number of tablets to be received up to the time of biopsy at week 24:

Tablets taken:

The total number of tablets taken corresponds to the sum of the number of tablet not returned compared to the number of pills dispensed.

If the date of last intake reported on the EOT form is  $\leq$  date of post-treatment biopsy then tables taken is equal to the number of tables taken up to Visit 3 (see definition above in section compliance at visit(i)).

If the date of last intake reported on the EOT form is  $>$  date of post-treatment biopsy then tables taken is equal to the number of tables taken up to Visit 3 (see definition above in section compliance at visit(i)) minus  $3 * (\text{Date of last intake reported on the EOT form} - \text{date of post-treatment biopsy})$ .

Tablets to be received up to the time of biopsy at week 24:

The total number of tablets to be received is equal to:

$$((\text{Date of biopsy at week 24} - \text{Study first treatment intake date} + 1) * 3)$$

- **Overall compliance at time of biopsy at week 24 (when biopsy results at week 24 are available) based on lanifibranor bottles**

The overall compliance based on lanifibranor bottles can be calculated as the actual number of lanifibranor tablets taken and the theoretical number of lanifibranor tablets to be received up to the time of biopsy at week 24:

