#### 4.1.4 *Patient management at the end of treatment*

The trial treatment is stopped after V3.

After the follow-up period (V4, 4 weeks after V3) the Investigator/hepatologists/general practitioner will decide according to each patient, the need to use the lifestyle changes recommendations whenever appropriate and treatment of comorbidities which may play a role in NASH such as, for example, diabetes and hyperlipidaemia.

If the study is positive there will be further trials for which these patients may be eligible.

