#### 4.4 Protocol deviations (PDs)

The list of PDs has already been developed (see Excel file appended to BDRM minutes named “INVEN\_21507\_Native\_Deviation”).

All PDs will be carefully identified through eCRF data before the BDRMs. During the BDRMs held before database lock (DBL), each PD will be classified as leading to exclusion from the PP population (“major”) or not leading to exclusion from the PP population (“minor”).

All PDs related to study inclusion or non-inclusion criteria, conduct of the trial, patient management or patient assessment will be described, such as:

- Violation of inclusion criteria
- Violation of exclusion criteria
- Intake of non-allowed concomitant medications during the treatment period
- Randomisation error
- Lack of compliance
- Primary endpoint not assessable (missing post-treatment biopsy results)
- Etc.

Additionally, the PDs that could not be identified through eCRF data will also be reviewed during the BDRMs. This listing will be based on the PD forms completed by the study monitors. These PDs will be extracted from the listing and imported in the database.

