**Lanifibranor tablets to be received up to the time of biopsy at week 24:**

The total number of lanifibranor tablets to be received is equal to:

- $((\text{Date of biopsy at week 24} - \text{Study first treatment intake date} + 1) \times 3)$  for patients receiving lanifibranor at the dose of 1200 mg
- $((\text{Date of biopsy at week 24} - \text{Study first treatment intake date} + 1) \times 2)$  for patients receiving lanifibranor at the dose of 800 mg

4.5.6.2 *Adverse Event data*

- **Treatment Emergent Adverse Event**

A Treatment Emergent Adverse Event (TEAE) corresponds to an Adverse Event (AE) that occurred on or after first dose of treatment up to 28 days post-last dose.

- **Treatment Emergent Adverse Events related to study treatment**

TEAE related to treatment is defined as a TEAE having a relationship to treatment equals to “Possibly related”, “Probably related” or with a missing relationship to study treatment.

Relationship equals to “Unlikely Related” will be considered as not related.

- **Non-Treatment Emergent Adverse Events (non-TEAEs)**

Non-TEAEs are AEs that occurred prior to treatment start.

- **Post-Treatment Adverse Events (PTAEs)**

PTAEs are AEs that occurred more than 28 days after end of treatment.

- **Serious Adverse Events**

By definition, a serious AE (SAE) is an AE that, at any time, fulfils one or more of the following criteria:

- results in death,
- is life threatening (the subject was at immediate risk of death at the time of the event; it does NOT refer to an event which hypothetically might have caused death if it were more severe),
- requires in-subject hospitalisation or prolongation of existing hospitalisation,
- results in persistent or significant disability/incapacity (substantial disruption of a person's ability to carry out normal life functions),
- is a congenital anomaly/birth defect,
- is any important medical event that may not be immediately life threatening or result in death or hospitalisation but, based upon appropriate medical judgment, may endanger the subject or may require intervention.

The seriousness of the event will be directly assessed by the investigator (specific variable within the AE database); therefore no derivation is needed.

- **Onset day**

Onset day is defined as the time between the first treatment intake date and AE onset date: (AE onset date – date of first intake + 1).

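### Compliance at time of biopsy counts tablets as due after treatment has stopped, so a late biopsy reads as missed doses in a descriptive table

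*SAP*

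**What the plan says.** SAP section 4.5.6.1 (Treatment data) defines several intake measures. The one at issue is the overall compliance at the time of the week 24 biopsy, calculated for patients with a biopsy result. It divides tablets taken by "the theoretical number of tablets to be received up to the time of biopsy at week 24".

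- **Tablets taken.** If the last intake is on or before the biopsy date, "tables taken is equal to the number of tables taken up to Visit 3" (the SAP prints tables for tablets). If the last intake is after the biopsy, 3 tablets are subtracted for each day between the two dates.
- **Tablets due.** The count is (biopsy date − first intake date + 1) × 3, with no cap at Visit 3 or at last intake.
- **Lanifibranor-bottle version.** After "The total number of lanifibranor tablets to be received is equal to", the SAP gives the same span to the biopsy date, × 3 at 1200 mg and × 2 at 800 mg. Its subtraction for a biopsy before the last intake is 3 a day at either dose.

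Protocol section 4.1.4 states: "The trial treatment is stopped after V3".

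Two neighbouring measures use other end dates: Compliance at Visit(i) counts tablets due to the visit date, and overall persistence counts them to the last intake. SAP section 5.3.1 lists all of these as descriptive statistics by treatment group in the safety set.

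**The concern.** The numerator and denominator cover different periods whenever the biopsy falls after Visit 3. The numerator is frozen at Visit 3, while the denominator grows by 3 tablets a day. The ratio then falls with biopsy delay as well as with missed doses, and the table cannot separate the two. A value of 92% could mean tablets left in the bottle or a biopsy booked two weeks late. If biopsy delay differed between arms, that would look like a difference in adherence.

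Such delays are foreseen. SAP section 4.3.5 names biopsies not done within 14 days of the last intake. Section 4.5.4.1.3 calls a biopsy available whenever the SAF activity score is non-missing for a biopsy reported at Visit 3, with no time limit, so the measure is still calculated for late biopsies. Biopsies from an early-termination Visit 3 also count (note in section 4.1.6.3).

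**Working it through.** The SAP states no compliance figure to reproduce, so the check applies its formula to a patient who misses no dose.

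**Inputs**
- 3 tablets a day, as in the SAP formula. A bracketed remark in section 4.5.6.1 says 3 tablets twice a day. It conflicts with the formula and must be reconciled; the figures here use the formula as written.
- First intake at V0 and last intake on the day of Visit 3, 168 days later (24 weeks): 169 dosing days, 507 tablets.
- d = days from Visit 3 (here also the last intake) to the biopsy.
- Supply: 5 kits × 3 bottles × 38 tablets = 570 (protocol section 4.3.2, Figure 4).

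**Formula:** compliance = (169 × 3) / ((169 + d) × 3) = 169 / (169 + d).

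| d (days) | Tablets taken | Tablets due | Compliance |
|---|---|---|---|
| 0 | 507 | 507 | 100% |
| 3 | 507 | 516 | 98.3% |
| 8 | 507 | 531 | 95.5% |
| 14 | 507 | 549 | 92.3% |
| 28 (illustration) | 507 | 591 | 85.8% |

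Three days is the visit window. Fourteen days is the limit the SAP generally uses for a biopsy under treatment; section 4.1.6.3 also gives 8 days, hence that row. With 165 to 171 dosing days the result is 92.2% to 92.4% at 14 days and 85.5% to 85.9% at 28 days.

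**Supply check.** At 28 days the tablets due (591) exceed everything dispensed (570).

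**Early stopper.** With a shorter course the same gap weighs more: 84 dosing days and a 14-day gap give 84/98 = 85.7%.

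**Bottle version.** At 800 mg the factor of 2 cancels, so the same percentages apply: 338/366 = 92.3% at 14 days. The subtraction rule adds a separate mismatch. Suppose an 800 mg patient takes 169 × 2 = 338 active tablets and is biopsied 3 days before the last intake. Tablets due are 166 × 2 = 332. The SAP subtracts 3 × 3 = 9, giving 329/332 = 99.1%. Subtracting the 2 × 3 = 6 active tablets taken in those days gives 332/332 = 100%.

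**After the fix.** With tablets due ending at the earlier of biopsy and Visit 3, every row of the table becomes 507/507 = 100%, which equals Compliance at Visit 3.

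**The case against.** **It is only descriptive.** This stands. No primary, sensitivity or secondary efficacy analysis in SAP section 5.2 contains a compliance term. The measure describes intake in patients with a biopsy result and is not formally related to response.

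**On-plan biopsies are barely affected.** This also stands. The biopsy belongs to Visit 3 with a window of ±3 days, and at 3 days the shortfall is under 2 points. The 28-day case is an illustration.

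**Persistence already gives the clean answer.** It ends at last intake, so the fully adherent patient scores 100% there, in the same table. That limits the harm but leaves the second measure wrong.

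**It may be meant as drug coverage up to the biopsy.** The SAP does not say so. It calls the measure compliance, and the denominator can exceed the whole supply. The SAP also trims the numerator when dosing continues past the biopsy, which suggests that matching periods were intended and the reverse case was missed.

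**A reader might infer that adherent patients lose their place in the per-protocol set.** SAP section 4.4 does list "Lack of compliance" among the deviations. However, it gives no threshold and names no variable there, the detailed list is in a file not shown, and each deviation is classified at blind review. Either of the other measures could be the basis. In addition, the per-protocol analysis of the primary endpoint uses observed cases under treatment, so biopsies beyond 14 days are already set to missing in it.

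**Conclusion.** The derivation is wrong as written, and the consequence is minor. For a patient who takes every tablet, the reported compliance falls short of 100% by 1.7 points for a biopsy 3 days after Visit 3 and by 7.7 points at 14 days. It falls further for later biopsies, for which the SAP sets no upper limit. These sizes assume 169 dosing days, a last intake on the day of Visit 3 and no missed dose.

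The damage is to the compliance lines by arm in section 5.3.1, where biopsy scheduling is mixed with missed doses. The primary test is not affected. The documents support neither of the two larger inferences: that adherent patients would be removed from the per-protocol set, or that an analysis of histological response is biased by this variable. They also give no reason to expect a difference in biopsy delay between arms.

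**What to change.** In SAP section 4.5.6.1:

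1. End tablets due at the earlier of the biopsy date and the actual Visit 3 date, including an early-termination Visit 3: (min(biopsy date, Visit 3 date) − first intake date + 1) × 3. In the bottle version use × 3 at 1200 mg and × 2 at 800 mg, as now.
2. State that days between the last intake and Visit 3 still count as due, as in Compliance at Visit(i). A patient who stops 14 days before a Visit 3 on day 169 and is biopsied that day then scores 155/169 = 91.7%, which reflects tablets not taken.
3. In the bottle version, make the daily subtraction for a biopsy before the last intake match the active tablets counted per day: 3 at 1200 mg and 2 at 800 mg.
4. Report the gap from last intake to biopsy by arm as its own variable.

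The cost is a few lines of SAP wording and a small change to the derivation code. The dates and tablet counts are already collected.
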